6.3.2.2 Part B

In Arm A: The first on-treatment visit should occur on Day 1 of the 1st CC-486 cycle (subject should receive the first CC-486 dose during the visit). Afterwards, visits will be done every 4 weeks \pm 3 days, during the CC-486 off period as close as possible to restarting the subsequent CC-486 cycle.

Additionally the subject will visit the clinic at time of each pembrolizumab infusion.

In Arm B: every 21 days \pm 3 days, prior to each pembrolizumab infusion

During the treatment period visits the following assessments will be done in both arms:

- Physical examination (symptom-oriented)
- ECOG PS

- Adverse events assessment
- Concomitant medication
- Laboratory assessments:
 - Hematology: Hemoglobin, Absolute Neutrophils Count (ANC) and Platelets
 - Blood chemistry: creatinine, AST, ALT, alkaline phosphatase, total bilirubin, glucose, TSH
 - Coagulation tests and pregnancy test: only if clinically indicated
 - CA-125
- Tumor burden assessments: if applicable according to sections 6.2 and 6.4.6.1
- Tumor biopsy (optional): if applicable according to sections 6.2 and 6.4.7.1.

Prior to the first dose of study treatment, there is no need to repeat hematology, blood chemistry and CA-125 tests provided they were done at screening within 7 days of randomization, unless deemed clinically required by the Investigator.

In Arm A, prior to each pembrolizumab infusion, there is no need to repeat laboratory tests unless clinically indicated and/or required according to the standard of care at the institution.

In Arm A only, hematology (hemoglobin, Absolute Neutrophils Count (ANC) and platelets) will be repeated at day 8, day 15 and day 22 (± 1 day) of each cycle. No clinical visit is required per protocol on these days. CC-486 dose adjustments, treatment withhold or treatment discontinuation based on hematology test results will be performed as per section 5.7.3.

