7: Hematology: Hemoglobin, Absolute Neutrophils Count (ANC), Platelets. Blood chemistry: creatinine, AST, ALT, alkaline phosphatase, total bilirubin, glucose, TSH. There is no need to repeat hematology and blood chemistry prior to the first dose of study treatment, provided that they were done at screening within 7 days prior to randomization, unless deemed clinically required by the Investigator. During treatment period: In Arm A, hematology will be done within 3 days of every visit prior to each CC-486 cycle and on Days 8, 15 and 22 (\pm 1 day). Blood chemistry will be done within 3 days of every visit prior to each CC-486 cycle. There is no need to repeat them prior to pembrolizumab administration unless clinically indicated and/or required according to the standard of care at the institution. In Arm B, hematology and blood chemistry will be done within 3 days of every visit prior to each pembrolizumab infusion.

8: There is no need to repeat CA-125 prior to first dose of study treatment provided that it was done at screening within 7 days of enrollment. Whenever possible, CA-125 should be tested at the same laboratory and with the same technique throughout the study. At the End of Treatment visit and during the follow-up, CA-125 will only be tested in subjects without irPD at time of study treatment discontinuation.

9: During the follow-up phase, only AEs and SAEs related to study treatments that are ongoing by the End of Treatment visit are to be reported and/or followed up (refer to section 6.3.4).

10: Concomitant treatments to be collected from date the PDCF is signed

11: Only concomitant treatments to treat AEs/SAEs related to study treatment will be recorded after the End of Treatment visit

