8.6 Safety Endpoints

The assessment of safety will be made on the safety population and will be based mainly on the frequency of adverse events. The latest version of the Medical Dictionary for Regulatory Activities (MedDRA) will be used to code all adverse events to a preferred term and system organ class. Adverse events will be graded using the Common Terminology Criteria for Adverse Events (NCI CTCAE v4.03) or according to the grading defined in section 5.7.1 if the adverse event is not specifically listed in NCI CTCAE. Subject's incidence of adverse events will be tabulated by system organ class, preferred term and toxicity grade by treatment arm. Adverse events leading to death or drug discontinuation, drug related and serious adverse events will also be summarized by treatment arm.

Detailed listings for all adverse events will also be provided.

Laboratory parameters: Laboratory parameters, graded according to the NCI CTCAE v4.03, will be summarized at baseline, along visits and at the end of study treatment by treatment arm. Tables of shifts in toxicity will also be provided.

Other Safety Data: Weight and ECOG will be summarized at baseline, along visits and at the end of study treatment by treatment arm. Tables of shifts in toxicity will also be provided when applicable.

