Statistical Analysis Plan

Protocol Title	Phase II randomized study of pembrolizumab with or without epigenetic modulation with CC-486 in patients with platinum-resistant epithelial ovarian, fallopian tube or primary peritoneal cancer
Protocol Number	TRIO026 (Part A) / NCT02900560
	
Revision	01
Product Name	CC-486
Indication	Platinum-resistant epithelial ovarian cancer (EOC), fallopian tube carcinoma (FTC) or primary peritoneal carcinomas (PPC)
Study Phase	II
Sponsor	TRIO
Version Date	10-Apr-2018

Confidentiality Statement

The information contained herein is confidential and proprietary and may not be disclosed, reproduced, or circulated without the prior written consent of TRIO.

Revision History

Not applicable; this is the initial version of the Statistical Analysis Plan.

List of Abbreviations

AE	Adverse Event
CI	Confidence Interval
CM	Concomitant Medications
EOC	Epithelial Ovarian Cancer
FTC	Fallopian Tube Carcinoma
GCIG	Gynecologic Cancer Intergroup
irCR	Immune-related Complete Response
irDCR	Immune-related Disease Control Rate
irNE	Immune-related Unevaluable
irORR	Immune-related Overall Response Rate
irPD	Immune-related Progressive Disease
irPR	Immune-related Partial Response
irRECIST	Immune-related Response Evaluation Criteria in Solid Tumors
irSD	Immune-related Stable Disease
ITT	Intent-to-treat
MedDRA	Medical Dictionary for Regulatory Activities
NCI CTCAE	National Cancer Institute Common Terminology Criteria for Adverse Events
PEM	Pembrolizumab
PPC	Primary Peritoneal Carcinomas
PT	Preferred Term
RDI	Relative Dose Intensity
SAE	Serious Adverse Event
SAP	Statistical Analysis Plan
SOC	System Organ Class
SSC	Study Steering Committee
TRIO	Translational Research in Oncology
WHODD	World Health Organization Drug Dictionary
ULN	Upper Limit of Normal

Title:

TRIO026 (Part A) – Statistical Analysis Plan

1. Introduction

This Statistical Analysis Plan (SAP) describes the detailed statistical methodology for executing the statistical analyses to assess the safety profile of CC-486, fertility evaluation as well as CA-125 response according to TRIO026 protocol version 2.0 for patients enrolled in Part A of the trial. Separate document(s) will be prepared to describe statistical analysis performed on Part B of this trial.

Statistical analysis will be performed by TRIO using SAS® software Version 9.4 or higher.

2. Study Design and Objectives

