3.5.3. Laboratory Values

Lab values will be converted to standard units and categorized according to NCI CTCAE version 4.03. Laboratory results not corresponding to NCI CTCAE terms will not be graded.

Hematology and serum blood chemistry will be summarized in descriptive statistics by calculating the mean, standard deviation, median, and range for the following:

- Baseline value
- Minimum post baseline value
- Maximum post baseline value

Shift tables in laboratory toxicity grades (comparing baseline grade with worst post-baseline grade) will be analyzed using standard shift tables, presenting number and proportion of patients and their maximum grade shift.

For laboratory tests without a toxicity grading scale, the shift table will present directional shifts from baseline to above or below the laboratory standard normal range using the maximum increase and/or decrease observed throughout the course of treatment/observation.

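### Part B schedules blood counts three times as often in Arm A as in Arm B, and no shift-table rule allows for it; a worst-grade rule would under-detect short cytopenias in Arm B

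*Protocol*

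**What the plan says.** Protocol section 6.3.2.2 adds counts in one arm: "In Arm A only, hematology (hemoglobin, Absolute Neutrophils Count (ANC) and platelets) will be repeated at day 8, day 15 and day 22". These are on top of the count taken before each 28-day CC-486 cycle. For the control arm, footnote 7 to Table 7 (section 6.2.2) says: "In Arm B, hematology and blood chemistry will be done within 3 days of every visit prior to each pembrolizumab infusion". Arm B visits are 21 days apart. The body of Table 7, its footnote 7 and section 6.3.2.2 agree with one another.

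The synopsis row on safety assessments, repeated in SAP Appendix 6.1, describes hematology as weekly and names no arm. That does not fit the sections above for Arm B.

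On analysis, Protocol section 8.6 says that graded laboratory parameters "will be summarized at baseline, along visits and at the end of study treatment by treatment arm", and adds: "Tables of shifts in toxicity will also be provided". It does not define which post-baseline value enters a shift, and it does not mention the different sampling. The SAP supplied covers Part A only. Its section 3.5.3 builds shift tables by "comparing baseline grade with worst post-baseline grade". For Part B its introduction says: "Separate document(s) will be prepared to describe statistical analysis performed on Part B of this trial".

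**The concern.** The worst of many values tends to be worse than the worst of few. If both arms had the same true cytopenias, the arm tested every 7 days would still show more of them than the arm tested every 21 days, whenever episodes can begin and end between two Arm B samples. A by-arm table of worst grade would then mix a difference in toxicity with a difference in looking.

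Hematology is where this matters most. The synopsis calls the main toxicity of CC-486 hematologic, and Protocol section 1.3.1 reports at least one myelosuppression event in about half of CC-486 patients. Section 3.2 says that Part B will compare the safety as well as the efficacy of the two arms. An excess of cytopenia in Arm A is therefore a contrast that readers will look for, and they should be able to tell how much of it could be detection.

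The weekly counts are not in question. They inform CC-486 dose decisions under section 5.7.3, and nothing here asks to change them.

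**Working it through.** The plan gives no figure for laboratory shifts, so there is none to reproduce.

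**1. Scheduled samples (Protocol Table 7 and section 6.3.2.2, no delays).** Counting from day 1, Arm A has nominal samples on days 8, 15, 22, 29 and so on, every 7 days. Arm B has days 22, 43, 64, 85 and so on, every 21 days.
- 12 weeks: 84/7 = 12 against 84/21 = 4.
- 24 weeks: 168/7 = 24 against 168/21 = 8.
- If treatment lasted as long as the median irPFS assumed in section 8.7 (a proxy): 6.4 × 30.4375 = 194.8 days, 27 samples in Arm A; 4 × 30.4375 = 121.75 days, 5 samples in Arm B. Longer exposure widens the gap beyond 3 to 1.

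**2. Chance of seeing one episode.** For an episode of d days starting at a random time, with samples every k days, the chance is q = min(1, d/k).
- 7 days: 100% weekly, 7/21 = 33% three-weekly.
- 14 days: 100% against 14/21 = 67%.
- 21 days or longer: 100% in both.

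The visit windows (±1 day, ±3 days) blur these figures; the 100% at exactly 7 days is nominal.

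**3. Spurious difference when true rates are equal.** The true rate and the episode length are assumptions; the documents give neither. If a proportion p has at least one episode over 24 weeks and onsets are Poisson, the proportion detected is 1 − (1 − p)^q.

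| True rate, both arms | Episode | Arm A detected | Arm B detected | Spurious excess (points) |
|---|---|---|---|---|
| 10% | 7 days | 10.0% | 1 − 0.9^(1/3) = 3.5% | 6.5 |
| 10% | 14 days | 10.0% | 1 − 0.9^(2/3) = 6.8% | 3.2 |
| 20% | 7 days | 20.0% | 1 − 0.8^(1/3) = 7.2% | 12.8 |
| 20% | 14 days | 20.0% | 1 − 0.8^(2/3) = 13.8% | 6.2 |
| 50% | 7 days | 50.0% | 1 − 0.5^(1/3) = 20.6% | 29.4 |
| 50% | 14 days | 50.0% | 1 − 0.5^(2/3) = 37.0% | 13.0 |
| any | 21 days | p | p | 0 |

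Over rates of 10% to 50% and episodes of 5 to 14 days the excess runs from about 3 to 29 points. A simulation of the same process agrees to within 0.3 points.

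**4. Dependence on Arm B's own rate.** With episodes of at least 7 days, the error is what Arm B misses. For 7-day episodes and an assumed Arm B rate of 2%: 2 − 100 × (1 − 0.98^(1/3)) = 1.3 points. For 5%: 5 − 100 × (1 − 0.95^(1/3)) = 3.3 points.

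**5. What a common 21-day grid does.** Arm B's days 22, 43, 64 and 85 fall on Arm A's cycle 1 day 22, cycle 2 day 15, cycle 3 day 8 and cycle 4 day 1, all scheduled Arm A samples. Each arm then has 4 samples in 12 weeks, and with equal true rates the spurious difference is zero. A real excess shrinks, however. With assumed true rates of 50% and 10% (difference 40 points):
- 7-day episodes: all samples 50.0 − 3.5 = 46.5; common grid 20.6 − 3.5 = 17.
- 14-day episodes: all samples 50.0 − 6.8 = 43; common grid 37.0 − 6.8 = 30.

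**The case against.** A reader might infer that Part B's shift tables will overstate Arm A's cytopenias. The documents do not support that as a statement of fact. The worst-grade rule stands in a SAP for Part A, where all cohorts share one hematology schedule, and Part B is left to separate documents. Section 8.6 speaks of summaries along visits, and section 6.3.2.2 requires no clinic visit on days 8, 15 and 22, so a visit-based table might leave those counts out. This stands, and the point is conditional because of it.

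A visit-based table is not a clean escape, though. Arm A clinic visits come every 4 weeks in the CC-486 off period, and Arm B visits every 21 days. That gives 84/28 = 3 samples against 4 in 12 weeks, with Arm A always at the same phase of its cycle. Such a table could err in the other direction.

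A second tempting inference is that a matched table should govern between-arm statements. Step 5 shows why not: in the 50% against 10% case with 7-day episodes, the all-samples table is 6.5 points too high and the matched one about 23 points too low.

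The stakes are also limited. Section 2.2.2 frames the safety objective around the combination, section 8.6 rests safety mainly on adverse event frequency, section 7.1.2 records a laboratory change as an adverse event only if the investigator finds it clinically relevant, and no laboratory hypothesis is tested. Section 1.3.2 names anemia as the only hematologic event among the most common with pembrolizumab, mostly low grade, so Arm B's rate of severe cytopenia may be low and the error small. All this keeps the point minor. It does not supply the missing rule.

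**Conclusion.** The point holds in conditional form and is minor. The 3 to 1 sampling ratio follows from the detailed schedule, and section 8.6 plans by-arm shift tables with nothing to account for it. If Part B adopts worst post-baseline grade, which is an inference from the Part A SAP, cytopenias shorter than 21 days will be under-detected in Arm B and part of any Arm A excess will be detection.

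The direction is clear under that rule; the size is not. It depends on episode length and on Arm B's true rate, neither of which the documents give. The assumed ranges above put it anywhere from zero (episodes of 21 days or longer), through 1 to 3 points (7-day episodes, Arm B rate 2% to 5%), to 29 points (7-day episodes, rate 50% in both arms). The conclusion also rests on the detailed sections rather than the synopsis: if weekly testing applied to both arms, the premise would fall.

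**What to change.** Leave the sampling as it is. In the Part B SAP:

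1. Define the post-baseline value used in the laboratory shift tables, and note that the arms are sampled at different intervals.
2. Add one supplementary worst-grade shift table restricted, in both arms, to the scheduled samples nearest study days 22, 43, 64, 85 and so on, over the same fixed time window. The fixed window is needed because matching sample dates does not correct for longer time on treatment in one arm. Study days serve better than infusion days: Arm A's first infusion is on day 8 and Arm B's is at treatment start, so an infusion-day grid gives Arm A days 8, 29, 50 and 71 against Arm B days 22, 43 and 64, that is 4 against 3 post-baseline samples by day 84. Taking the nearest scheduled sample also copes with delayed cycles and infusions.
3. Show this table beside the all-samples table and cite both in any between-arm statement. The matched table must not replace the full one.

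Separately, reconcile the synopsis wording on weekly hematology with section 6.3.2.2 and Table 7.

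The cost is one extra table and no extra blood samples. That table uses fewer Arm A values and so attenuates a real absolute excess, which is why it is supplementary.

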6.3.3 End of Treatment Visit

End of Treatment visit must be scheduled 30 days (± 7 days) after the last administration of the last study drug.

The primary purpose of this visit is to follow-up any AEs ongoing at the time of discontinuation and to assess any new AEs that may have occurred since discontinuation.

During the End of Treatment visit the following assessments will be done:

- Physical examination (symptom-oriented)
- ECOG PS
- Hematology and Blood chemistry
- CA-125 (only in subjects without irPD at time of study treatment discontinuation)
- Adverse events assessment
- Concomitant medication

In Part A only, the End of Treatment will be the last study visit for all subjects except those who:

- Discontinue treatment for reasons different than irPD
- Discontinue treatment for any reason and have ongoing SAEs (regardless of relationship with study treatment) or study treatment-related AEs at time of the End of Treatment visit

6.3.4 Follow-up Visits

6.3.4.1 Part A

The subjects that will enter the follow-up phase are those who:

- a) Discontinue treatment for reasons different than irPD: These subjects will enter the follow-up phase and will be followed up to assess response/progression (with tumor burden assessments and CA-125) every 12 weeks (± 1 week) until irPD. After irPD, and provided that subject has undergone the End of Treatment visit, all subjects will be taken off the study unless requiring AE/SAE follow-up according to the paragraph (b) below.
- b) Discontinue treatment for any reason and have ongoing SAEs (regardless of relationship with study treatment) or study treatment-related AEs at time of the End of Treatment visit: Monitoring of these events will continue as clinically indicated until the events have resolved (or return to baseline) or in the Investigator's opinion, are unlikely to resolve due to the nature of the condition and/or the subject's underlying disease. Frequency of visits will be according to Investigator judgment.

6.3.4.2 Part B

All subjects will be followed-up.

Subjects discontinued from study treatment for reasons different than progressive disease per irRECIST (e.g. unacceptable toxicity, Investigator's decision, etc.) will be followed up to assess response/progression (with tumor burden assessments and CA-125) every 12 weeks (± 1 week) until irPD.

Once irPD is declared, all subjects will be followed for survival every 6 months (through visit or phone contact) until death or for at least 1 year after the End of Treatment visit, to assess the survival status.

Any AE or SAE related to study treatments that is ongoing by the End of Treatment visit, must be followed up to resolution or until the events have resolved (or return to baseline) or in the Investigator's opinion, are unlikely to resolve due to the nature of the condition and/or the subject's underlying disease.

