Indication	Platinum-resistant epithelial ovarian cancer (EOC), fallopian tube carcinoma (FTC) or primary peritoneal carcinomas (PPC)
Study Duration	
Part A:
 
 ▪ Accrual: 24 months ▪ Treatment phase: 6 months ▪ Follow-up: According to subject’s status at End of Treatment 
Part B:
 
 ▪ Accrual: 24 months ▪ Treatment phase: 6 months ▪ Follow-up: 12 months
Sponsor / Participating Investigator	This is a TRIO-sponsored study, led by [name] (Professor of Medicine, Jonsson Comprehensive Cancer Center, UCLA, USA) as Study Chair. The study is financially supported by Celgene Corporation.
Participating Investigator Sites	
Part A: 4 sites in 1 country (USA)
 
Part B: approximately 25 sites in 2 countries (USA and Germany; includes sites participating in Part A)

Target Population	The target study population consists of adult patients with platinum-resistant/refractory EOC/FTC/PPC who have received a maximum of 2 prior treatment regimens for the platinum-resistant/refractory relapse (definition of platinum resistant/refractory disease will be based on the platinum-free interval following frontline chemotherapy). Subjects must have previously received platinum-based chemotherapy (intravenous and/or intraperitoneal) following and/or preceding debulking surgery. They will be required to have measurable disease according to irRECIST (Immune-related Response Evaluation Criteria in Solid Tumors) for Part A. For Part B, subjects will be required to have either measurable and/or non-measurable disease. They will also be required to have a life expectancy of at least 6 months, Eastern Cooperative Oncology Group (ECOG) Performance Status (PS) of 0-1, adequate liver, renal and bone marrow functions; absence of known autoimmune diseases, of certain bone marrow conditions and of serious diseases which could affect protocol compliance or the interpretation of study results.

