Background and Rationale	
There are approximately 200,000 new cases of EOC diagnosed each year in the world and this is the leading cause of death from gynecologic cancer in the United States and in many other countries.
 
More than 75% of patients present with advanced disease at primary diagnosis. The current standard initial therapy is debulking surgery followed by platinum-based doublet chemotherapy administered either intravenously and/or intraperitoneally. Neoadjuvant chemotherapy is being increasingly used.
 
Despite aggressive surgery and frontline chemotherapy, most patients with advanced disease experience a relapse. Patients with a platinum-free interval of less than 6 months are considered to have platinum-resistant disease and those that recur/progress while receiving frontline chemotherapy are considered to have platinum-refractory disease. At first relapse, approximately 25% of patients have platinum-resistant/refractory ovarian cancer and their prognosis is poor, with a median overall survival of approximately 12 months. All current treatment options have a response rate of < 15-20%. There is a clear, unmet medical need for effective treatments for patients with platinum-resistant/refractory relapsed EOC.
 
Recent advances in immunotherapy have led to the development and rapid introduction into clinical practice of monoclonal antibodies directed against two immune checkpoints, CTLA-4 (Cytotoxic T-lymphocyte-associated antigen-4) and PD-1 (Programmed death protein 1) (or PD-L1, Programmed death-ligand 1). All of these agents, and in particular the anti-PD-1 antibodies, have shown clear benefit in the treatment of metastatic melanoma and non-small cell lung cancer (NSCLC). Moreover, responses have been of long duration, suggesting that the immune system may be adaptive and to some extent being able to counteract the development of treatment resistance. Immune checkpoint inhibitors have recently demonstrated encouraging signs of antitumor activity for patients with pretreated advanced ovarian cancer.
 
It is known that epigenetic modifications in gene expression associated with methylation and de-acetylation of DNA and histones occurs in human malignancies and can be associated with disease progression and resistance to treatment. Epigenetic therapies with either hypomethylating agents, such as azacitidine, or histone deacetylase (HDAC) inhibitors have been shown to be of benefit in the treatment of some malignancies. More recently, exciting data have emerged indicating that treatment with azacitidine may increase the response to anti-PD-1 therapy in patients with NSCLC, suggesting that hypermethylation may in part explain failure to respond to immune checkpoint inhibition.
 
Pre-clinical research investigating the effects of epigenetic therapy (azacitidine and/or HDAC inhibitors) on gene expression in human cancer cell lines has identified a group of relevant genes whose expression

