	
The CA-125 response rate is defined as the proportion of subjects having a CA-125 response according to the GCIG criteria.
 
Part B
 
The immune-related Progression-Free Survival (irPFS) is defined as the time from the date of randomization until the date of progression (assessed by irRECIST) or death due to any cause, whichever occurs first, as per Investigator assessment. Progression will be based on tumor assessment made by the Investigators according to the irRECIST criteria. Progression will not be declared on the basis of CA-125 alone.
 
The immune-related Duration of Response (irDoR) is defined as the time (in months) from the date when irPR or irCR is first met (whichever status comes first) and the date of irPD or death, whichever occurs first (as per Investigator assessment).
 
irORR, irDCR and CA-125 response rate as described above.
 
Overall Survival (OS) defined as the time (in months) from randomization to death from any cause.

--	---

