3.5 Study End

The study will end once the last subject undergoes the last visit and all events required for the final analyses have been observed and collected.

The trial may be prematurely terminated by the sponsor. In this case, subjects deriving clinical benefit from the study treatment at time of trial termination will continue to be provided with study drug by the sponsor/manufacturer.

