6.5.2 Discontinuation from Study Participation

The primary reason for study participation discontinuation should be documented on the eCRF. Reasons for subject's discontinuation from the study include:

- Death
- Consent withdrawal from entire study participation
- Subject completes the follow-up period as per protocol sections 6.3.3 and 6.3.4
- Subject non-compliance
- Lost to follow-up

Should a subject decide to withdraw consent, all efforts will be made to complete and report the observations as thoroughly as possible. The Investigator should contact the subject by telephone or through a personal visit to establish as completely as possible the reason for the withdrawal. A complete final evaluation at the time of the subject's withdrawal should be made with an explanation of why the subject is withdrawing from the study. After complete withdrawal of consent, no further study procedure will be performed and no further data will be collected after the date of the subject's withdrawal from study.

Partial withdrawal occurs when the subject withdraws consent but agrees to be contacted for further information on survival. It should be documented in both the medical records and the eCRF that the subject agreed to be contacted for information on survival despite the subject's withdrawal of informed consent. Partial consent withdrawal is not considered a discontinuation from study participation.

In the case a subject does not show up for study visits, site staff should make reasonable contact attempts before declaring the subject as lost to follow-up. These attempts need to be documented in the medical records.

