8.8 Timing of Analysis

The primary analysis in Part A will be conducted once 5 subjects in each cohort are considered evaluable for response. Subjects will be considered evaluable once they have completed at least 2 CC-486 cycles, have undergone the 1st post-baseline tumor burden assessment and both tumor biopsies performed and adequate paired tissue obtained.

The primary analysis in Part B will be performed once at least 142 events of disease progression or death have been observed, or at the end of study whichever occurs first. The trial may be prematurely terminated by the sponsor. An interim analysis is planned when 50% of expected events are observed (i.e., 71 events); safety analysis will also be performed at this time. There are no plans to terminate the study early; the interim analysis is performed to support ongoing resourcing activities.

In Part B, a follow-up analysis will be performed one year after the primary analysis. Both efficacy and safety analysis will be performed.

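### Part B requires survival follow-up only to one year after each subject's own End of Treatment visit, so OS events can be lost before the planned follow-up analysis

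*Protocol*

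**What the plan says.** - **Length of survival follow-up.** Protocol 6.3.4.2 has all Part B subjects contacted every 6 months once irPD is declared, "until death or for at least 1 year after the End of Treatment visit". Section 3.2, Table 7 footnote 4 and the synopsis (Efficacy Assessments) carry the same rule. The synopsis (Study Duration) gives, for Part B, "Follow-up: 12 months".
- **When the clock starts.** Section 6.3.3: "End of Treatment visit must be scheduled 30 days (± 7 days) after the last administration of the last study drug". The required minimum is therefore about 13 months after the last dose.
- **Leaving the study.** Section 6.5.2 lists, among the reasons for ending participation, "Subject completes the follow-up period as per protocol sections 6.3.3 and 6.3.4".
- **Analyses.** Section 8.8 puts the primary Part B analysis at 142 irPFS events or the end of study, whichever comes first, and adds that "a follow-up analysis will be performed one year after the primary analysis", covering efficacy and safety.
- **The endpoint.** OS is a Part B secondary endpoint (2.2.2, 8.5), "defined as the time (in months) from randomization to death from any cause" (synopsis, Statistical Methods). The documents give no OS censoring rule, event target or common cut-off. The SAP covers Part A only and leaves Part B to separate documents.

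**The concern.** OS is normally censored at one calendar cut-off, so that how long a subject is followed depends on when she entered and not on how she is doing. Here the required follow-up runs from the end of her own treatment. A subject who stops early may leave the study about 13 months later; one who stays on treatment is followed for longer.

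Time on treatment is related to prognosis. Treatment ordinarily ends at irPD, but section 5.5 also ends it for toxicity, investigator decision or completion of the maximum pembrolizumab course, and in Arm A permanently stopping either drug stops both. The censoring time can therefore differ by arm. For a subject who stops without irPD, the year may already have run out when irPD is declared.

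Two things are at stake: OS deaths that are never recorded, which makes the planned follow-up analysis less useful for OS, and some bias in the later part of the survival curves. A Part B SAP written later can set a censoring rule but cannot recover survival status that was not collected.

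**Working it through.** **1. The plan's own design figure.** Inputs from Protocol 8.7: irPFS hazard ratio 4/6.4 = 0.625, two-sided alpha 0.05, power 80%. Schoenfeld: 4 × (1.960 + 0.842)² / (ln 0.625)² = 142.1, matching the 142 events in 8.8. With exponential irPFS, 24 months of uniform accrual and 46 months in total, the event probabilities are 0.995 and 0.967 (mean 0.981). Rounding up to 143 events, 143/0.981 = 145.8, or 72.9 per arm, matching 73. The documents give no comparable figure for OS, so the rest is conditional.

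**2. Model for OS (assumed).** Exponential time to progression with medians 4 and 6.4 months, then exponential post-progression survival with median m, chosen to give an assumed median OS. Treatment ends at progression, End of Treatment is one month later, and every site stops at the minimum, 12 months after that. Median permitted follow-up is 4 + 13 = 17 months in the control arm and 6.4 + 13 = 19.4 months in the combination arm.

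A death is missed if post-progression survival exceeds 13 months: share = 2^(−13/m).

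The control median of 12 months is the background figure for patients at first resistant relapse, "with a median overall survival of approximately 12 months"; it is not a Part B assumption. The combination medians are assumptions: no OS gain (12), the 2.4-month irPFS gain carried over (14.4), and the irPFS hazard ratio carried over (12/0.625 = 19.2).

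| Arm, median OS | m | Deaths missed | Deaths per 75 by month 46: common cut-off → minimum | 24-month OS: true → Kaplan-Meier under minimum |
|---|---|---|---|---|
| Control, 12 | 5.99 | 22% | 69.8 → 57.5 | 0.156 → 0.173 |
| Combination, 12 | 3.67 | 9% | 69.6 → 64.8 | 0.160 → 0.175 |
| Combination, 14.4 | 5.52 | 20% | 66.5 → 56.9 | 0.231 → 0.254 |
| Combination, 19.2 | 9.57 | 39% | 58.1 → 42.8 | 0.382 → 0.411 |

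**3. Sensitivity.**
- Control, median OS 12: 25% with no End of Treatment gap (2^(−12/5.99)); 19% if progression is found only at 12-weekly scans; 11% if sites in fact continue 6 months beyond the minimum (2^(−19/5.99)).
- Control, median OS 10 or 15: 12% or 36%.
- Over control OS 10 to 15, combination OS 12 to 19.2, with or without scan delay, and 0 or 10% dying before progression: about 7% to 40%.
- If OS were independent of irPFS: 31% to 47%.

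Some deaths would be missed anyway. With a common cut-off at month 46, 7% of control deaths fall later. The rule itself loses (69.8 − 57.5)/69.8 = 18% of the control deaths that had occurred by then.

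**4. Follow-up analysis.** With 150 subjects, 142 irPFS events are expected near month 37, which puts the follow-up analysis near month 49. Taking post-progression median 6.3 months in both arms (OS medians 12.3 and 15.4), deaths in the two arms together are:
- common cut-off: 116 at month 37, 138 at month 49 (22 added);
- stopping at the minimum: 101 and 111 (10 added).

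**5. Effect on OS estimates.** The rule censors nobody before month 13, so 12-month OS and a 12-month median are unchanged. At an OS median of 19.2 the Kaplan-Meier median becomes 19.8. The 24-month estimate is too high by 1.5 to 2.9 points in the table. The direction follows from who is removed: subjects who progressed early leave, while those still at risk include subjects not yet progressed.

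**The case against.** The strongest reply is that the text sets a floor and not a stopping rule. Section 8.8 plans a later efficacy analysis, and section 3.5 keeps the study open until the last subject's last visit and until "all events required for the final analyses have been observed and collected". Section 6.5.2 names completion of follow-up as a reason to leave but sets no maximum. This stands in part: a reader might infer that follow-up does stop at one year, or that a quarter of deaths will go unrecorded, and the documents support neither. What they support is that sites may stop at one year. The 12-month follow-up in the synopsis points that way, and the only event counts given for any analysis are for irPFS.

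A reader might also take the censoring time to be progression plus 13 months. The clock starts at End of Treatment, so it is time on treatment that matters; the model in the working does not include stopping for toxicity or other reasons.

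The bias is also small. At 75 per arm, the standard error of a 24-month OS of 0.156 is √(0.156 × 0.844/75) = 4.2 points, against a bias of 1.7; at 0.382 it is 5.6 points, against 2.9. In the model of step 4, the OS hazard ratio at month 58 moves only from about 0.74 to 0.72. All of this stands, and it is why the lost events, and not the bias, are the main cost.

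Finally, the Part B analysis rules are still to be written, and section 3.2 allows an amendment before Part B. But the same section lets this protocol version run unchanged into Part B, so the collection rule is best corrected here.

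**Conclusion.** The point holds as a gap in the data-collection rule. Required survival follow-up ends at a subject-specific date, no common OS cut-off is set, and nothing ties follow-up to the analysis planned one year after the primary analysis.

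If sites stop at the minimum, about 7% to 40% of deaths could go unobserved across plausible scenarios, and about 20% to 25% in the control arm if its median OS is 12 months. These shares rest on exponential times, treatment ending at progression and every site stopping at the minimum, so none should be read as a prediction. The 12-month OS estimate is unaffected, the median moves little, and 24-month OS is overestimated by roughly 2 to 3 points.

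OS is secondary with no stated power. The primary irPFS analysis is unaffected, because tumour assessment continues to irPD after treatment stops. This is a worthwhile low-cost improvement and not a fault in the main comparison.

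**What to change.** Replace the survival follow-up rule in the synopsis (Study Duration and Efficacy Assessments), 3.2, 6.3.4.2 and Table 7 footnote 4. Every randomised Part B subject should be followed for survival every 6 months until death, full consent withdrawal or the common data cut-off of the follow-up analysis, whichever comes first. State that OS is censored at the last date known alive on or before that cut-off, and carry this into the Part B SAP. The synopsis must change with the rest, or its 12-month figure would contradict the new rule. Section 6.5.2 can stand, since it points to 6.3.4.

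Cost: a few more 6-monthly contacts, by phone as the protocol already allows, for subjects alive beyond one year after End of Treatment.
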